#### **Differences from CDC umbrella protocol**

This protocol was adapted from a generic protocol approved by CDC entitled, "Assessing COVID-19 seroprevalence from routine antenatal care visits," approved on 12/17/2020 (eClearance ID: 0900f3eb81c55548). No major methodological changes were made. Minor differences made in response to local feedback include:

- Prevalence estimates at district level rather than health facility level
- Twenty women each will be recruited from 40 health facilities among 4 districts each month compared to 30 women from 30 health facilities
- First visit ANC routine lab tests (HIV, syphilis, Hepatitis B, and/or malaria) will be recorded on the questionnaire
- Per guidance from the CDC-Atlanta team, several questions on potential exposure were removed from the questionnaire and COVID-19 vaccination history was added (compared to the generic protocol questionnaire)

## Acronyms

Acronym	Explanation
ANC	Antenatal Care
CIDRZ	Centre for Infectious Disease Research in Zambia
CDC	U.S. Centers for Disease Control and Prevention
CHWs	Community Health Workers
COVID-19	Coronavirus Disease
DHO	District Health Office
DBS	Dry Blood Spot
HIV	Human Immunodeficiency Virus
IRB	Institutional Review Board
MNCH	Maternal, Newborn and Child Health
MOH	Ministry of Health
MTA	Materials Transfer Agreement
NAAT	Nucleic Acid Amplification Test
NHRA	National Health Research Authority
ODK	Open Data Kit
PEPFAR	U.S. Presidential Emergency Plan for AIDS Relief
PHO	Provincial Health Office
PMTCT_STAT	Prevention of Mother to Child Transmission of HIV
PPE	Personal Protective Equipment
QA/QC	Quality Assurance/ Quality Control
SARS-CoV-2	Severe Acute Respiratory Syndrome-Related Coronavirus-2
SOPs	Standard Operating Procedures
UNZA BREC	University of Zambia Biomedical Research Ethics Committee
VTM	Viral Transport Media
ZNPHI	Zambia National Public Health Institute

## 1.0 Introduction

### 1.1 General information on research topic

The novel coronavirus SARS-CoV-2, the cause of COVID-19, was first detected in Wuhan city, China in December 2019 and the first cases were confirmed in Zambia in March 2020.

Current data suggest that as many as 50% of cases are asymptomatic [1]. Initial surveillance has focused primarily on patients with symptoms or severe disease, and, as such, the full spectrum of the disease, including the extent and fraction of mild or asymptomatic infections that do not require medical attention are not clear. Estimates of the case fatality ratio, and other epidemiological parameters, will likely be lower than current estimates once the full spectrum of disease is able to be included in the denominator. With any novel virus, such as SARS-CoV-2, initial population seroprevalence is assumed to be negligible. Thus, antibody seropositivity in a population can allow inferences to be made about the extent of infection, the cumulative incidence of infection in the population, and trends in infection over time.

This protocol proposes to investigate the extent of SARS-CoV-2 infection, as determined by seropositivity, among pregnant women attending 1st antenatal care (ANC) visits, as a surrogate for the prevalence in the general population. The utility of ANC-based surveillance has been established for malaria [2-5], and there is no evidence to date suggesting that pregnant women are at higher risk of contracting SARS-CoV-2 than non-pregnant adults, suggesting that ANC-based surveillance could provide useful information for monitoring the spread of SARS-CoV-2 over time [6]. This will be a non-randomized assessment of the potential to leverage pregnant women attending 1st ANC as a pragmatic sentinel population to monitor prevalence of SARS-CoV-2 and to detect changes in transmission in selected areas.

As the Zambian Ministry of Health (MOH) continues to focus on controlling and mitigating further spread of the SARS-CoV-2 through active surveillance for case detection, contact tracing, physical distancing and isolation while strengthening case-based management, it is important to build a national SARS-CoV-2 surveillance system that is crucial for containing transmission of the virus and preparing for future waves of the infection.

## **1.2 Overview of research and research gaps**

This surveillance platform may be able to provide key information on the spread of the SARS-CoV-2 virus through the general population. By using serologic testing to understand trends in the proportion of pregnant women over time who were exposed to SARS-CoV-2, we will be able to understand not only the ultimate proportion of pregnant women who were ever infected, but also be able to track and potentially detect outbreaks (e.g. in areas with increasing positivity rates), unlike data that would be available from a single cross-sectional survey, which could give the overall prevalence at a single point in time. In most places to date, testing has focused on symptomatic people, their contacts or others considered at high risk for infection, but there is limited understanding of the true proportion of asymptomatic cases.

There are gaps in information about the prevalence and clinical characteristics of SARS-CoV-2 in Zambia. We propose to conduct SARS-CoV-2 sentinel surveillance among first-time ANC attendees in selected Maternal, Newborn and Child Health (MNCH) departments in four districts (Lusaka, Chongwe, Chadiza and Chipata) of Lusaka and Eastern provinces to assess SARS-CoV-2 seroprevalence. Pregnant women will serve as a proxy for the healthy adult population of these districts, much as they have in sentinel surveillance for HIV and malaria. Because we will use serologic testing from blood and not nasal swabs, this collection will not substantially alter the risk for either the health worker nor the woman and will not deplete the supplies of SARS-CoV-2 Polymerase chain reaction (PCR) reagents used for diagnosis.

## **1.3 Overall purpose of the research**

The purpose of this project is to provide information on the seroprevalence of SARS-CoV-2 antibodies in the community with pregnant women as the sentinel population. CIDRZ will work with facility in-charges in the selected sentinel sites to provide sensitization and SARS-CoV-2 antibody testing to pregnant women presenting for their first ANC visit.

## 2.0 Statement of the Problem

Zambia is experiencing a SARS-CoV-2 epidemic. From March 18, 2020 to February 19, 2021, a total of 73,203 confirmed cases have been reported in Zambia. However, the true number is likely much larger, because surveillance systems for SARS-CoV-2 in Zambia are incomplete [7]. ANC surveillance of SARS-CoV-2 antibodies could provide needed insights into transmission trends in the general population. This surveillance will provide a means to systematically detect SARS-CoV-2 antibodies in pregnant women and notify relevant authorities about the prevalence.

## 3.0 Rationale/ Justification

Since 2020, the coronavirus disease has become a major public health concern and sustainable and efficient surveillance platforms are urgently needed; assessing women attending 1st ANC should provide insights into transmission trends in the general population. This activity will determine what proportion of pregnant women demonstrate evidence of SARS-CoV-2 infection over time. The findings of this research may be used to change the way health system monitors the epidemic and ensures health services are made available with minimal disruptions.

## 4.0 Literature Review

ANC surveillance has not been routinely utilized for SARS-CoV-2 in any country. A cross-sectional study from Cape Town, South Africa found a seroprevalence of 38% among residual serum from antenatal clinic attendees in July and August 2020 [8]. Six African countries including Zambia (i.e., Kenya, Malawi, Mozambique, Nigeria, Uganda, and Zambia) are piloting ANC surveillance based on experience for surveillance of other infectious diseases (HIV, syphilis, malaria) [9,10]. ANC surveillance has been a key strategy for HIV for many years, because women attending ANC clinics represent an accessible healthy population [11-13].

Prevalence estimates of SARS-CoV-2 infections have varied widely throughout Africa. This is likely a result of varying time, study population, and study design [14-20]. Nevertheless, SARS-CoV-2 infections are under-reported because of the large asymptomatic proportion of

infections, testing limitations, and surveillance gaps [21,22]. Africa is no exception, where several prevalence surveys (including in Zambia) have shown under-ascertainment of SARS-CoV-2 infections [7,23]. For instance, during a population-based study in six districts in Zambia in July 2020, the ratio of reported cases to estimated infections ranged from 1:1012 (Livingstone District) to 1:21 (Lusaka District) [7]; overall, only 1 case was reported for every 92 infections. In Cape Town, 5% of residual serum specimens from persons living with HIV and women attending ANC clinics testing positive for SARS-CoV-2 antibodies had positive PCR test results in the public health surveillance system [24]. Other studies from other African countries have revealed substantial under-ascertainment of SARS-CoV-2 infections [18,25-27]. Strategies for improvement in surveillance have been called for by the Africa CDC and others [28,29].

## 5.0 Research questions

This study will assess the seroprevalence of SARS-CoV-2 in pregnant women aged 15-49 years who present to the health facility for their first antenatal care visit. This surveillance will answer the following research question: “What is the seroprevalence of antibodies to SARS-CoV-2 among pregnant women attending first ANC visit in Zambia?”

## 6.0 Research Aims and Objectives

### 6.1 Research Aim

The primary aim of this activity is to determine SARS-CoV-2 seroprevalence from women attending antenatal clinics for their first ANC visit as an easy-access population for routine monitoring.

### 6.2 Primary Objectives

- 6.2.1 To estimate on a monthly basis the seroprevalence of SARS-CoV-2 among pregnant women aged 15-49 years attending their first ANC visit at selected health facilities in Chadiza, Chipata, Chongwe, and Lusaka districts of Eastern and Lusaka Provinces.
- 6.2.2 To monitor trends in SARS-CoV-2 seroprevalence in the selected districts.

### **6.3 Secondary Objectives**

- 6.3.1 To determine the feasibility and acceptability of SARS-CoV-2 antibody tests among pregnant women
- 6.3.2 To estimate the prevalence of HIV-COVID 19 co-infection among pregnant women aged 15-49 years
- 6.3.3 To determine sociodemographic factors associated with SARS-CoV-2 seropositivity among pregnant women
- 6.3.4 To compare trends in seroprevalence among pregnant women with routine surveillance data to determine if ANC sentinel surveillance is a viable surveillance strategy for SARS-CoV-2

## **7.0 Methodology**

### **7.1 Study Design**

This will be a passive surveillance of pregnant women attending their first antenatal care visit at the selected study sites in the four selected districts. Pregnant women attending 1st ANC will be used as a pragmatic sentinel population to monitor the seroprevalence of SARS-CoV-2 over time. Women will be informed of this activity during group health education sessions and will be consented during individual HIV testing and counselling. To minimize discomfort to the participant, spots of blood will be collected from all women consenting to participate (up to 20 women per study site per month) on filter paper for a SARS-CoV-2 serologic test using a finger prick or a venous blood draw, depending on the method being used to obtain blood for routine HIV and syphilis testing during first ANC visits. In addition, women will be asked to respond to a short questionnaire. The woman's name will not be included on the sample or on the form; rather, a unique study ID will be used to link the questionnaire to the sample. Seroprevalence data will be aggregated at the district level on a monthly basis.

### **7.2 Study Site and Population**

#### **7.2.1 Study Sites**

Study sites will be selected in each of four purposively selected districts using a probability-proportional-to-size selection of 10 eligible facilities within each district. Eligible facilities will

have averaged at least 19 first ANC visits per month over the course of the previous year.

Surveillance activities will be implemented in two urban and rural districts as follows:

Table 1: Study sites and sampling interval for SARS-CoV-2 seroprevalence surveillance in ANC clinics in Chadiza, Chipata, Chongwe, and Lusaka Districts - Zambia				
District		Facility	Average monthly ANC attendance (2020)*	Sampling interval
Chadiza	1	Chanida Rural Health Centre	19	1
	2	Nsadzu Rural Health Centre	21	1
	3	Madzaela Health Post	21	1
	4	Bwanunkha Rural Health Centre	23	1
	5	Chanjowe Health Post	24	1
	6	John Rural Health Centre	24	1
	7	Mkumbuzi Rural Health Centre	28	1
	8	Zemba Rural Health Centre	36	1
	9	Chadiza Rural Health Centre	44	2
	10	Miti Rural Health Centre	46	2
Chipata	1	Champhande Rural Health Centre	21	1
	2	Chikando Rural Health Centre	23	1
	3	Lunkwakwa Urban Health Centre	25	1
	4	Mwami Hospital Affiliated Health Centre	28	1
	5	Chipata Hospital Affiliated Health Centre	34	1
	6	Jerusalem Rural Health Centre	35	1
	7	Walela Health Post	56	2
	8	Mchini Health Post	69	3
	9	Namseche Rural Health Centre	92	4
	10	Kapata Urban Health Centre	162	8
Chongwe	1	Nchute Health Post	19	1
	2	Chikumbi Health Post	22	1
	3	Kasisi Rural Health Centre	23	1
	4	Palabana Rural Health Centre	24	1
	5	Kanakantapa Rural Health Centre	27	1
	6	Water Falls Rural Health Centre	28	1
	7	Katoba Rural Health Centre	32	1
	8	Chainda Rural Health Centre	35	1
	9	Ngwerere Main Rural Health Centre	109	5
	10	Chongwe Referral Rural Health Centre	137	6
Lusaka	1	Coptic Hospital	21	1
	2	Kuku Health Post	98	4
	3	Chainda Urban Health Centre	99	4
	4	Matero Main Urban Health Centre	228	11

12

5	Chaisa Urban Health Centre	231	11
6	Kanyama West Health Post	246	12
7	George Urban Health Centre	371	18
8	Matero First Level Hospital	407	20
9	Kanyama First Level Hospital	572	28
10	University Teaching Hospital - Adult	606	30

\* Based upon PMTCT\_STAT indicator from PEPFAR MER

### 7.2.2 Study Population

A sample of 20 pregnant women attending their first ANC visit at the selected study sites will be enrolled into the study until the monthly sample size is reached.

## 7.3 Selection of Participants, Sampling and Sample Size

### 7.3.1 Selection of Participants

Women presenting to the selected study sites for their first ANC visit at selected health facilities in the four districts will be eligible to participate in the study. A facility-specific interval for systematic sampling will be defined based on each facility's monthly mean number of women attending their first ANC visit based on the historic monthly ANC attendance during fiscal year 2020. until the monthly sample size is met at a given facility.

Data will be collected over a 12-15 months period of implementation to ensure that the number of required samples are met in all implementing sites.

#### 7.3.1.1 Inclusion criteria

All women presenting to the selected study sites will be considered for inclusion into the study if they are:

- Confirmed pregnant and are registered for their first ANC visit
- Aged 15 to 49 years
- Able to provide consent to participate and have blood sample collected for the SARS-CoV-2 antibody test

[figure not shown]
#### 7.3.1.2 Exclusion criteria

- Not first ANC visit for the pregnant woman
- Women less than 15 years or above 49 years old
- Women not able to provide consent for study participation

### 7.3.2 Sample Size

All pregnant women who meet the eligibility criteria presenting at the study sites will be approached for participation into the study. Monthly ANC attendance varies by district, as shown in Table 2. Study districts will be expected to recruit 200 pregnant women per month. The estimated seroprevalence is expected to vary by study site, as prevalence has been demonstrated to be different between urban and rural locations in Zambia [7]. A sample size of 200 women per district per month will be sufficient to detect a range of estimated proportions of SARS-CoV-2 seroprevalence (Figure 1). The confidence interval (CI) reflects the bounds of the true seroprevalence of COVID-19 among pregnant women attending ANC (and not the overall pregnant women population or general population). Where prevalence is expected to be low (i.e. rural districts), a sample size of 200 women produces a 95% CI half-width of 2.4% for 3% seroprevalence (lowest estimate). Where prevalence is expected to be higher (i.e. urban districts), a sample size of 200 women produces a 95% CI half-width of 7.0% for 50% seroprevalence. Women will be recruited evenly throughout the month from study sites selected for each district. If the monthly recruitment target is met, study sites will be expected to pause sample collection and reconvene at the start of the next month.

Table 2: Average monthly number of first ANC attendees using PMTCT_STAT denominator	
District	Average monthly ANC attendance
Chadiza	424
Chipata	759
Chongwe	653
Lusaka	6,378

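### Section 7.3.2 has every eligible woman approached, which contradicts the systematic sampling in 7.3.1 and the Table 1 intervals at 17 of 40 sites, with the main consequence in Lusaka

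*Protocol*

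**What the plan says.** Three places in the protocol point to interval sampling:

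- Section 7.3.1: "A facility-specific interval for systematic sampling will be defined based on each" facility's mean monthly number of first ANC visits in fiscal year 2020. The text then breaks off and resumes with an orphaned clause, "until the monthly sample size is met at a given facility".
- Section 7.2.1, Table 1, is titled "Study sites and sampling interval for SARS-CoV-2 seroprevalence surveillance in ANC clinics" and gives one interval for each of the 40 named sites.
- Section 7.3.2: "Women will be recruited evenly throughout the month from study sites selected for each district".

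One sentence, also in section 7.3.2, says otherwise: "All pregnant women who meet the eligibility criteria presenting at the study sites will be approached for participation into the study". The same section adds that once the monthly target is met, "study sites will be expected to pause sample collection and reconvene at the start of the next month". Sections 7.1 and 7.2.2 set the quota at 20 women per site per month. Nothing in the protocol limits the women approached to those selected by the interval.

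**The concern.** The 7.3.2 sentence is an instruction about whom to approach. It is not a restatement of eligibility, which 7.3.1.1 already covers. At the University Teaching Hospital site, Table 1 has every 30th woman selected and 7.3.2 has every woman approached.

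Approaching everyone up to a quota of 20 and then pausing means that a busy site recruits only from the opening days of each month. The first primary objective is "To estimate on a monthly basis the seroprevalence of SARS-CoV-2 among pregnant women aged 15-49 years", and section 7.1 states: "Seroprevalence data will be aggregated at the district level on a monthly basis". A sample drawn from the first days of the month does not estimate the month's level when seroprevalence is moving. The distortion would also differ between districts, because site sizes differ. No later analysis can recover late-month attendees who were never sampled.

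**Working it through.** **Inputs.** Attendance *a* and interval *k* come from Table 1, and the quota of 20 per site from 7.1 and 7.2.2. Assumptions, not in the protocol: a 30-day month, even arrivals, attendance as in Table 1, and a consent proportion *p* varied from 0.5 to 1.

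**Reproducing the plan's figures.** *k* = floor(*a*/20), with a minimum of 1, reproduces all 40 printed intervals. For example, 606/20 = 30.3 gives 30, and 98/20 = 4.9 gives 4. The intervals were therefore built to spread 20 women over the month.

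**Where the two rules differ.** Intervals above 1: Chadiza 2 sites, Chipata 4, Chongwe 2, Lusaka 9, in total 17 of 40. At the other 23 sites the interval is 1 and the rules agree.

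**Time to fill the quota.** Everyone approached: 30 × min(1, 20/(*a·p*)) days. Table 1 interval: 30 × min(1, 20*k*/(*a·p*)) days. For the nine Lusaka sites:

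| Attendance | Interval | All approached, p = 1 | All approached, p = 0.5 | Table 1 interval, p = 1 |
|---|---|---|---|---|
| 98 | 4 | 6.1 | 12.2 | 24.5 |
| 99 | 4 | 6.1 | 12.1 | 24.2 |
| 228 | 11 | 2.6 | 5.3 | 28.9 |
| 231 | 11 | 2.6 | 5.2 | 28.6 |
| 246 | 12 | 2.4 | 4.9 | 29.3 |
| 371 | 18 | 1.6 | 3.2 | 29.1 |
| 407 | 20 | 1.5 | 2.9 | 29.5 |
| 572 | 28 | 1.0 | 2.1 | 29.4 |
| 606 | 30 | 1.0 | 2.0 | 29.7 |

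**Coverage of the month.** This is the mean over a district's ten sites of the fraction of the month elapsed when the quota fills. If seroprevalence rises linearly by 1 point over the month, the true monthly mean sits at 0.5 and the sample mean at coverage/2. The lag is therefore 0.5 − coverage/2. The part due to the 7.3.2 sentence is (coverage under Table 1 − coverage if all approached)/2. At *p* = 1:

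| District | All approached | Table 1 | Attributable lag per 1-point rise |
|---|---|---|---|
| Lusaka | 0.179 | 0.939 | 0.380 |
| Chipata | 0.548 | 0.794 | 0.123 |
| Chongwe | 0.659 | 0.806 | 0.073 |
| Chadiza | 0.760 | 0.849 | 0.044 |

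The coverage still missing under Table 1 comes from rounding intervals down and from the cap of 20. It is not caused by the contradiction.

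**Sensitivity to consent, Lusaka.** Coverage (all approached / Table 1) is 0.193/0.980 at *p* = 0.9, 0.204/1.000 at 0.8, 0.219/1.000 at 0.7 and 0.267/1.000 at 0.5. The attributable lags are 0.394, 0.398, 0.391 and 0.367, so the result hardly depends on consent.

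**In points, Lusaka.** For assumed within-month rises of 1, 2, 5 and 10 points, 0.38 × rise gives 0.4, 0.8, 1.9 and 3.8 points.

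**The case against.** The strongest reply is that the protocol leaves little real doubt. The section on selecting participants prescribes the interval, Table 1 prints it for each site, and the sample-size section itself asks for even recruitment. For harm to occur, staff would have to follow one loose sentence against all of these, and 7.4.1.4 promises SOPs on screening and enrolment. This stands as an argument about likelihood. It does not remove the contradiction: those SOPs are still to be written from this text, and the recruitment procedure in 7.4.2.1 never mentions the interval.

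Second, the bias figures rest on assumed rises. Against the 7.0-point half-width that 7.3.2 gives for 200 women at 50% seroprevalence, the lag is about a quarter for a 5-point rise (1.9/7.0 = 0.27) and about half for a 10-point rise (3.8/7.0 = 0.54). Under a steady rise it also largely cancels from the month-to-month trend in objective 6.2.2. Both points are fair and limit the severity. However, a systematic shift does not average out as sampling error does, and it remains in the monthly level.

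Third, some large sites outside Lusaka would also fill early: Kapata in 600/162 = 3.7 days, Chongwe Referral in 600/137 = 4.4 and Ngwerere in 600/109 = 5.5. That is correct. The emphasis on Lusaka holds for district averages, not for every site.

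Finally, the quota wording in 7.1 and 7.2.2 does not mention the interval. It is compatible with interval sampling, so it needs no change. The exact cause of the broken sentence in 7.3.1 is a guess, most likely a stray full stop, and the finding does not depend on it.

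**Conclusion.** The concern holds. The 7.3.2 sentence is wrong as written: at 17 of 40 sites it cannot be followed together with 7.3.1 and Table 1, and at large sites it conflicts with the even recruitment required in its own section. That conclusion needs no assumption.

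The consequence is conditional on sites acting on the sentence. In that case the Lusaka estimate, and its comparison with the other districts, would reflect mainly the first week of each month at full consent. The size of the bias depends on a within-month change that the protocol does not give. The number of women recruited and the stated half-widths are unaffected. This should be corrected before site instructions are written, but it does not undermine the design.

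**What to change.** In 7.3.2, replace the sentence with: *Eligible women selected by the facility's sampling interval (Table 1) will be approached for participation.*

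In 7.3.1, repair the orphaned clause to read: *Women will be selected at this interval until the monthly sample size is met at a given facility.*

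Keep the Table 1 intervals, and keep the pause as a cap. The cost is two sentences of protocol text, with the same sites, quota and tests and no added staff time.

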## **7.8 Data analysis**

Data will be analyzed on a monthly basis using a statistical program. Basic descriptive statistics, by district, including prevalence point estimates, confidence intervals, and relative standard errors will be tabulated. Variance and confidence intervals will be adjusted for health facility clustering. Prevalence estimates will be disaggregated by sociodemographic variables, routine ANC lab results, and risk factors.

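### The half-widths in section 7.3.2 (2.4 points at 3%, 7.0 at 50%) assume simple random sampling, whereas the design samples facilities and section 7.8 plans cluster-adjusted intervals

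*Protocol*

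**What the plan says.** - **Precision (Protocol 7.3.2).** The monthly target is 200 women per district: "Study districts will be expected to recruit 200 pregnant women per month". At the upper end of the expected range, "a sample size of 200 women produces a 95% CI half-width of 7.0% for 50% seroprevalence"; at the lower end the stated half-width is 2.4 points at 3% seroprevalence. No ICC, design effect or effective sample size is given.
- **Sampling (7.1, 7.2.1).** Sites come from a "probability-proportional-to-size selection of 10 eligible facilities within each district", and each contributes up to 20 women a month.
- **Level of reporting.** The list of differences from the umbrella protocol includes "Prevalence estimates at district level rather than health facility level", and 7.1 aggregates results by district each month.
- **Analysis (7.8).** "Variance and confidence intervals will be adjusted for health facility clustering".
- **Expected heterogeneity (7.3.2).** Seroprevalence is expected to differ from site to site because "prevalence has been demonstrated to be different between urban and rural locations in Zambia". Table 1 lists both kinds of site within one district: Chipata has "Kapata Urban Health Centre" and one other urban health centre alongside several rural ones.
- **Target (6.2.1).** The primary objective concerns women "attending their first ANC visit at selected health facilities in Chadiza, Chipata, Chongwe, and Lusaka districts", which could be read as limiting inference to the sampled sites.

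**The concern.** When a district estimate is built from 10 sampled facilities, its variance has a between-facility part that does not shrink as more women are taken from the same sites. A half-width from the binomial variance of 200 independent women leaves that part out; a cluster-adjusted interval includes it. Sections 7.3.2 and 7.8 thus describe the uncertainty of one estimate on two different bases.

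These are the only precision figures in the text, and they support the claim that 200 women per district per month are enough for the monthly estimates of objective 6.2.1. A reader would expect about 7 points either side of an estimate near 50%, and the monthly reports could show clearly wider intervals.

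**Working it through.** **Inputs from the protocol.** n = 200 per district per month; 10 facilities with m = 20 women each; p = 3% and 50%; 95% confidence. Facility attendance is from Table 1 and district attendance from Table 2. **Assumed:** ICC of 0.01 to 0.10, as the protocol gives none.

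**1. Reproducing the stated figures.** Simple random sample: half-width = 1.96 × √(p(1−p)/200).
- p = 3%: 1.96 × √(0.03 × 0.97/200) = 2.36 points
- p = 50%: 1.96 × √(0.25/200) = 6.93 points

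A t critical value on 199 df gives 2.38 and 6.97, which round to the stated 2.4 and 7.0. The ratio (7.0/6.93)² is about 1.02. Read as a design effect, that implies an ICC of 0.02/19 ≈ 0.001, so the rounding hides no allowance for clustering. A simple finite-population correction would have given 5.0 (Chadiza), 6.0 (Chipata), 5.8 (Chongwe) and 6.8 (Lusaka) at 50%, so none was applied.

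**2. The basis of section 7.8.** Design effect (DEFF) = 1 + (20 − 1) × ICC; half-width = critical value × √(DEFF × p(1−p)/200). The between-facility SD is √(ICC × p(1−p)).

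| ICC (assumed) | DEFF | Effective n | Facility SD at 50% / 3% | Half-width at 50% | Half-width at 3% |
|---|---|---|---|---|---|
| 0.01 | 1.19 | 168 | 5.0 / 1.7 | 7.6 | 2.6 |
| 0.02 | 1.38 | 145 | 7.1 / 2.4 | 8.1 | 2.8 |
| 0.05 | 1.95 | 103 | 11.2 / 3.8 | 9.7 | 3.3 |
| 0.10 | 2.90 | 69 | 15.8 / 5.4 | 11.8 | 4.0 |

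These use z = 1.96. With t on 9 df (10 clusters minus 1; critical value 2.262), the ranges are 8.7 to 13.6 at 50% and 3.0 to 4.6 at 3%.

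**3. What an ICC of this size means.** Suppose 2 of the 10 Chipata sites had 20% seroprevalence and 8 had 10%. The mean is 12% and ICC = 0.2 × 0.8 × 0.10²/(0.12 × 0.88) = 0.015, so DEFF = 1.29. At 30% and 10% the mean is 14% and ICC = 0.2 × 0.8 × 0.20²/(0.14 × 0.86) = 0.053, so DEFF is about 2.0.

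**4. Finite-population correction at both stages (not planned).** The selected sites hold 286/424 = 67% of district attendance in Chadiza, 545/759 = 72% in Chipata, 456/653 = 70% in Chongwe and 2,879/6,378 = 45% in Lusaka. Multiply the between-facility term by (1 − share) and each site's within term by (1 − 20/attendance), set to zero where attendance is below 20. Half-widths at 50%:

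| ICC | Chadiza | Chipata | Chongwe | Lusaka |
|---|---|---|---|---|
| 0.02 | 4.2 | 5.2 | 4.7 | 7.0 |
| 0.05 | 5.2 | 5.8 | 5.5 | 8.0 |
| 0.10 | 6.5 | 6.8 | 6.6 | 9.4 |

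This is approximate, because attendance shares stand in for the first-stage correction under probability-proportional-to-size selection.

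**5. If only the selected facilities are the target.** Facilities are then strata, and only within-facility variance counts. At ICC 0.05: 1.96 × √(0.25 × 0.95/200) = 6.8 points.

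**6. Month-to-month change.** The same facilities recur, so stable facility effects cancel. At ICC 0.05 and 50%, the half-width of a difference is 1.96 × √(2 × 0.95 × 0.25/200) = 9.6, against 1.96 × √(2 × 0.25/200) = 9.8 under simple random sampling.

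**The case against.** The best case for the protocol has four parts.

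- **Finite-population correction offsets the clustering.** In Chadiza, Chipata and Chongwe the ten sites hold about 70% of attendance, and many are nearly fully enumerated. With correction at both stages the half-width stays at or below 6.8 points even at ICC 0.10. This stands as a statement about real precision for a given month's attendees. It does not rescue section 7.3.2, because no such correction is planned or used there, and in Lusaka the corrected width still passes 7.0 once the ICC exceeds about 0.02.
- **The evidence for heterogeneity lies elsewhere.** The urban/rural mix visible in Table 1 is in Chipata, whereas the excess that survives correction is in Lusaka, where no site is labelled rural. This is fair, and the size in Lusaka is unknown. Section 7.3.2 does, however, expect prevalence to vary by site without limiting that to any district.
- **The ICC is assumed.** This also stands. At 3% prevalence an ICC of 0.10 means a facility SD of 5.4 points, larger than the mean, so the top of that range is strained. The 9-df figures change the critical value as well as the variance and are not like for like with 7.0.
- **The arithmetic is right and nothing hangs on it.** The figures are correct for a simple random sample, no decision rule depends on them, and section 7.8 already supplies the adjustment. This limits the consequence. It does not put the two sections on one basis.

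Reading objective 6.2.1 as confined to the selected sites does not resolve the matter either. The 7.0 would then hold, but the clustering adjustment in 7.8 would be on the wrong basis. Probability-proportional-to-size selection and district-level reporting point to a district target.

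**Conclusion.** The point holds. The half-widths in section 7.3.2 carry a design effect of about 1 and are not those of the cluster-adjusted intervals planned in section 7.8. For a district target without finite-population correction, any positive ICC makes the stated figures too favourable: by 0.6 to 4.8 points at 50% (7.6 to 11.8 against 7.0) and by 0.2 to 1.6 points at 3% (2.6 to 4.0 against 2.4), over an assumed ICC of 0.01 to 0.10. The size cannot be fixed from the protocol.

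The fault is in the stated planning precision. The planned analysis produces no wrong interval because of it, and the precision of month-to-month differences does not suffer where facility effects are stable. It should be corrected, but it is not a reason to change the design.

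**What to change.** In section 7.3.2:

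1. State whether the target is all first-visit antenatal attendees in the district or only women at the selected facilities.
2. For a district target, restate the half-widths as critical value × √(DEFF × p(1−p)/n) with DEFF = 1 + 19 × ICC, over a stated ICC range such as 0.01 to 0.10. Name the critical value and any finite-population correction, and use the same choices in section 7.8.
3. If the target is the selected facilities only, keep the stated figures, describe facilities as strata, and change section 7.8 to match.
4. Redraw Figure 1 if it also assumes simple random sampling; it was not available for checking.
5. Add a sentence that these widths apply to a single monthly district estimate and not to month-to-month change, because the same facilities recur.

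The cost is one reworded paragraph and possibly one figure (with a matching edit to 7.8 if needed). The only downside is a less favourable stated precision. Enrolment stays as planned.
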